5. STUDY CONDUCT

5.1. Participant Enrollment and Randomization

The investigator (or designee) will ensure:

- Signed informed consent is obtained from each potential participant before any study specific procedures are performed.
- Each potential participant is assigned a unique enrollment number at screening upon signing the Informed Consent.
- The eligibility of each participant is in accordance with the inclusion and exclusion criteria.
- Each eligible participant is assigned a unique randomization code.

Randomization will be done on Day 1 before IMP dosing. Randomization codes will be assigned strictly sequentially as participants become eligible for randomization (codes to be used without leading zeros). Randomization numbers will be generated within the AstraZeneca randomization system (AZRand).

The enrollment number will be used to identify the participant during the screening process and throughout study participation, if applicable, and will be recorded in the eCRF. This number will be composed of two parts: the first part will have 4 digits (fixed) representing the study Clinical Unit site identifier. The second part will have 3 digits (ascending) which will be assigned sequentially within each study Clinical Unit starting with 001.

If a participant withdraws his/her participation in the study, then his/her enrollment/randomization code cannot be reused. For each treatment sequence, an additional set of random numbers will be generated with AZRand.

5.1.1. Re-screening

Rescreening is permitted only with the prior approval of the Medical Monitor if the participant has not met the eligibility criteria within the screening period and/or the reason for screen failure was transient (including but not limited to study equipment failure, unforeseen personal events that mandate missed screening visit). Each participant can be re-screened only once. A second re-screening is allowed for participants who do not meet inclusion criterion 4, per investigator discretion and prior approval of the Medical Monitor. Re-screened participants should be assigned the same participant number as for the initial screening. Participants who are re-screened are required to sign a new Informed Consent. All procedures from screening should be repeated.

5.1.2. Procedures for Randomization

Upon completion of the randomization request form, the randomization list will be produced by the IRT vendor according to AZRand and participants will be randomized using IRT.

An IRT will be used for randomization to a treatment group and assignment of IMP kit numbers. A participant is considered randomized into the study when the investigator notifies the IRT that the participant meets eligibility criteria and the IRT provides the assignment of the IMP kit numbers to the participant.

Specific information concerning the use of the IRT will be provided in a separate manual.

The number of participant identifiers generated for the study will account for the required number of randomized participants per the sample size calculation (N = 207, see Section 11.4).

5.2. Procedures for Handling Incorrectly Randomized Participants

Participants who fail to meet the inclusion criteria or meet any exclusion criterion should not, under any circumstances, be randomized into the study. There can be no exceptions to this rule.

Where a participant, who does not meet the selection criteria, is randomized in error and this is identified before dosing, the participant should be withdrawn from the study. If a participant is withdrawn prior to dosing they will be replaced.

If a participant, who does not meet the selection criteria, has been dosed before the error is identified, the participant should be advised to continue follow-up visits and safety assessments to ensure their safety. The investigator will inform the AstraZeneca Lead Physician of the error immediately.

5.3. Blinding and Procedures for Unblinding the Study

This is an open label study and blinding is not applicable.

The randomization lists should be kept in a secure location until database lock.

5.4. Study Intervention

Study intervention is defined as any investigational intervention(s), marketed product(s) or placebo intended to be administered to a study participant according to the study protocol.

5.4.1. Investigational Products

Details on the identity of the investigational product are presented in [Table 5-1](#).

Table 5-1 **Investigational Products**

Treatment Group	Treatment A	Treatment B	Treatment C
Formulation	AZD7442 co-formulation of AZD8895 + AZD1061 clonal cell line material in the same vial 20 mM histidine/histidine-HCl, 220 mM arginine-HCl, 0.04% (w/v) polysorbate80, pH 6.0	AZD8895 and AZD1061 clonal cell line material in separate vials 20 mM histidine/histidine-HCl, 240 mM sucrose, 0.04% (w/v) polysorbate80, pH 6.0	AZD8895 and AZD1061 cell pool material in separate vials 20 mM histidine/histidine-HCl, 240 mM sucrose, 0.04% (w/v) polysorbate80, pH 6.0
Strength/ Concentration	75 mg/mL AZD8895 + 75 mg/mL AZD1061; ie, 150 mg/mL total protein in a single vial	100 mg/mL AZD8895 and 100 mg/mL AZD1061 in separate vials	100 mg/mL AZD8895 and 100 mg/mL AZD1061 in separate vials
Dose	300 mg AZD7442 co-formulation as a single IM injection (1 × 2 mL IM injection)	150 mg AZD8895 and 150 mg AZD1061 as two IM injections (1 × 1.5 mL IM injection of each, two injections total)	150 mg AZD8895 and 150 mg AZD1061 as two IM injections (1 × 1.5 mL IM injection of each, two injections total)
Dosage level	Single dose (300 mg total protein)		
Route of administration	IM injection		
Use	Experimental		
IMP and NIMP	IMP		
Sourcing	Provided centrally by the sponsor		
Packaging and labeling	The IMP components will be provided in vials. Each vial will be labeled per country requirement.		

IM: intramuscular; IMP: investigational medicinal product; HCl: hydrochloric acid; NIMP: non-investigational medicinal product.

Details of the batch numbers will be included in the Trial Master File and the final CSR.

Treatment A

AZD7442 will be supplied by AstraZeneca as a solution for injection. AZD7442 300 mg will be supplied in a single vial containing 75 mg/mL AZD8895 and 75 mg/mL AZD1061, 20 mM histidine/histidine-HCl, 220 mM arginine-HCl, 0.04% (w/v) polysorbate-80, pH 6.0. The label-claim volume for AZD7442 is 2 mL.

Treatment B

AZD7442 will be supplied by AstraZeneca as solutions for injection. AZD7442 300 mg will be supplied in two vials, one containing 100 mg/mL AZD8895 and one containing 100 mg/mL AZD1061, both in 20 mM histidine/histidine-HCl, 240 mM sucrose, 0.04% (w/v) polysorbate-80, pH 6.0. The label-claim volume for each vial is 1.5 mL.

Treatment C

AZD7442 will be supplied by AstraZeneca as solutions for injection. AZD7442 300 mg will be supplied in two vials, one containing 100 mg/mL AZD8895 and one containing 100 mg/mL AZD1061, both in 20 mM histidine/histidine-HCl, 240 mM sucrose, 0.04% (w/v) polysorbate-80, pH 6.0. The label-claim volume for each vial is 1.5 mL.

All formulations will be provided as sterile, clear to opalescent, colorless to yellow solutions.

5.4.2. Supply of Investigational Product

The IMP will be supplied by AstraZeneca as cartons containing one vial of either AZD7442, AZD8895 or AZD1061.

A release document signed by a legally authorized Qualified Person in EU/UK or Pharmacist in US at the study Clinical Unit will be placed in the appropriate section of the Trial Master File to document labeling and dispensing of the investigational product(s) to the participant.

Dispensing and retention of reserve BE samples of investigational product will be performed in accordance with the FDA Code of Federal Regulations 21, Part 320 Bioavailability and Bioequivalence requirements.

5.4.3. Labeling

Labels will be prepared in accordance with GMP and local regulatory guidelines.

5.4.4. Storage and Handling Procedures

AZD7442 vials are stored at 2°C to 8°C (36°F to 46°F) and must not be frozen. The investigator, or an approved representative (eg, pharmacist), will ensure that all study intervention is stored in a secured area, in refrigerated temperatures (2°C to 8°C; 36°F to 46°F) and in accordance with applicable regulatory requirements. A temperature log will be used to record the temperature of the storage area. Temperature excursions outside the

permissible range listed in the clinical supply packaging are to be reported to the monitor upon detection. A calibrated temperature monitoring device will be used to record the temperature conditions in the drug storage facility. Storage conditions stated in the IB may be superseded by the label storage.

AZD7442 must be kept in original packaging until time of preparation to prevent prolonged light exposure.

The dose of AZD7442 must be prepared by the investigators or site's designated study intervention manager using aseptic technique. Total time from needle puncture of the study intervention vial to the start of administration must not exceed:

- 24 hours at 2°C to 8°C (36°F to 46°F).
- 4 hours at room temperature.

If the final product is stored at both refrigerated and ambient temperatures, the total time must not exceed 24 hours otherwise a new dose must be prepared from new vials. AZD7442 vials do not contain preservatives; any unused portion of the vial must be discarded immediately after use.

AstraZeneca will be permitted upon request to audit the supplies, storage, dispensing procedures and records, provided that the blind of the study is not compromised.

5.4.5. Dose and Treatment Regimens

Each participant will receive a single IM dose of AZD7442 on Day 1 after randomization to one of the three treatment groups ([Table 5-2](#)). Additionally, within each of the treatment groups, participants will be randomized 1:1:1 to injection sites of lateral thigh (vastus lateralis), gluteal dorsal, or gluteal ventral.

Participants receiving Treatment A will be administered a dose via a single IM injection from a single drug product vial.

Participants receiving Treatment B or Treatment C will be administered a dose via two separate IM injections, each from a separate drug product vial containing AZD8895 or AZD1061. AZD8895 is administered first, followed by AZD1061. If a participant experiences an immediate hypersensitivity reaction after receipt of the first IM injection, but before the second IM injection, further IMP should not be given.

Participants will be allowed to drink water until 45 min to 1 hour before dosing to prevent dehydration. Water and food will be allowed ad libitum from 1 hour after the start of dosing.

After dosing, participants will remain semi-supine on their bed or sitting (except when necessary for study procedures) until completion of the Day 1 assessments.

Other restrictions, including posture control are described in Section 4.2. Data of participants may be excluded from the PK analysis set as described in Section 11.1.3.

5.4.6. Dose Preparation and Administration

Each vial selected for dose preparation should be inspected. If there are any defects noted with the IMP, the investigator and site monitor should be notified immediately.

No incompatibilities between AZD7442 and PC or PP syringes have been observed.

Commonly used needles for IM injections are of 22 – 25 gauge and 1 – 1.5 in (25 – 38 mm) length and can be selected based on characteristics of each patient according to standard procedures for IM injections ([US CDC 2022](#)).

The study intervention does not contain preservatives and any unused portion must be discarded.

AZD7442 preparation and the doses to be administered are given in [Table 5-2](#).

Table 5-2 AZD7442 Preparation and Administration

Treatment	Product	Formulation	Number of Vials	Injection Volume	Dose Level
A	Test	Co-formulation of AZD8895 and AZD1061 clonal cell line material in a single vial	1	2.0 mL (single IM injection)	300 mg total protein of AZD7442 (150 mg each of AZD8895 and AZD1061)
B	Reference (when compared with Treatment A) or test (when compared with Treatment C)	AZD8895 and AZD1061 clonal cell line material in two separate vials	2 (1 vial AZD8895 + 1 vial AZD1061)	1.5 mL each (two IM injections)	
C	Reference	AZD8895 and AZD1061 cell pool material in two separate vials	2 (1 vial AZD8895 + 1 vial AZD1061)	1.5 mL each (two IM injections)	

Note: All treatments will be administered as IM injections either in the lateral thigh, gluteal dorsal, or gluteal ventral.

5.4.6.1. Treatment A: Co-formulation of AZD8895 and AZD1061 Clonal Cell Line Material in a Single Vial

Obtain one vial of co-formulated AZD7442 for administration and equilibrate to room temperature prior to use.

Accurately withdraw 2 mL of co-formulated AZD7442 into a single appropriately sized syringe.

Administer the co-formulated AZD7442 as a single 2 mL IM injection in the appropriate region (lateral thigh, gluteal dorsal, or gluteal ventral) according to standard procedures for IM injections.

5.4.6.2. Treatment B: AZD8895 and AZD1061 Clonal Cell Line Material in Separate Vials

AZD7442 must be administered as separate injections to the participant in sequential order, with no participant receiving a dose of AZD8895 without also receiving the matching dose of AZD1061.

Obtain one vial each of AZD8895 and AZD1061 clonal cell line material for administration and equilibrate to room temperature prior to use.

Accurately withdraw 1.5 mL of AZD8895 into an appropriately sized syringe. Accurately withdraw 1.5 mL of AZD1061 into a separate appropriately sized syringe.

Administer the injections of AZD7442 (AZD8895 and AZD1061) with an appropriate needle according to standard procedures for IM injections in the appropriate region (lateral thigh, gluteal dorsal, or gluteal ventral). AZD8895 must be administered first in the appropriate region followed by AZD1061 in the second region on the opposite side.

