4.5.2 Safety analysis set (SAF)

[figure not shown]
[figure not shown]
The safety analysis set will include all participants who were randomized and received any amount of IMP.

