4.5.3 PK analysis set (PKS)

The PK analysis set will consist of all participants in the safety analysis set who received IMP and have evaluable serum PK data, with no important protocol deviations thought to impact on the analysis of the PK data.

Data from participants for whom the pre-dose concentration is > 5% of their respective Cmax for AZD8895 or AZD1061 may be excluded from the summary tables and figures and from the statistical analysis.

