4.10.2 Serum Concentrations

For the individual mAbs AZD8895 and AZD1061, as well as for the sum of the individual mAbs of AZD7442 (AZD8895 + AZD1061), the serum concentrations for each scheduled time point will be summarized by treatment group, treatment group and injection site, treatment group and bodyweight category, and treatment group, injection site, and bodyweight category using appropriate descriptive statistics, based on the PKS. A listing of all concentration-time data, ie, PK scheduled times, actual sample collection times, sample actual relative times, as well as derived sampling time deviations will be presented by treatment group (with injection site, and bodyweight category listed) for all participants in the SAF.

For AZD7442 concentration derived as the sum of AZD8895 and AZD1061 concentrations, the following cases of <LLOQ hold:

AZD1061 concentration	AZD8895 concentration	Result of AZD7442 concentration
<LLOQ	<LLOQ	<LLOQ
<LLOQ	XX	XX
YY	<LLOQ	YY
YY	XX	YY+XX
Missing	XX	Missing
YY	Missing	Missing
Missing	Missing	Missing

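### Protocol 5.4.6.2 and 5.4.6.3 rule out AZD8895 without AZD1061, yet 5.4.5 withholds the second injection after a reaction; the texts must be reconciled, and the PK handling of a half-dosed participant is left open

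*Protocol*

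**What the plan says.** **Dosing.** In Treatments B and C each mAb comes from its own vial, and Protocol 5.4.5 fixes the order: "AZD8895 is administered first, followed by AZD1061". Sections 5.4.6.2 (Treatment B) and 5.4.6.3 (Treatment C) use the same words: the injections must be given in sequence, "with no participant receiving a dose of AZD8895 without also receiving the matching dose of AZD1061". Neither section states an exception. Section 5.4.5 provides for one event: "If a participant experiences an immediate hypersensitivity reaction after receipt of the first IM injection, but before the second IM injection", then "further IMP should not be given". The sections do not refer to each other on this point.

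**Analysis.**
- The safety set has no minimum dose: "The safety analysis set will include all participants who were randomized and received any amount of IMP" (SAP 4.5.2).
- The PK analysis set is drawn from the safety set and needs evaluable serum data, "with no important protocol deviations thought to impact on the analysis of the PK data" (SAP 4.5.3; Protocol 11.1.3 agrees). It has no complete-dose condition.
- SAP 4.6.2 counts as important those dosing deviations likely to affect the primary endpoint. It says important deviations may, not must, lead to exclusion. SAP 4.5.8 leaves the decision to a classification meeting.
- SAP 4.10.2 has a table of rules "For AZD7442 concentration derived as the sum of AZD8895 and AZD1061 concentrations". If AZD1061 is below the limit of quantification and AZD8895 is measurable, AZD7442 is set to the AZD8895 value.

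**The concern.** The Protocol foresees hypersensitivity. It is an adverse event of special interest in 6.3.1.3, and 6.3.6 requires treatment for it to be at hand. If a reaction occurs between the injections, staff have two instructions that cannot both be met as written. The pairing rule is phrased as a must and stands in the administration steps; the withholding rule is phrased as a should and stands in the regimen section. That is the main point, and it concerns participant safety.

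The secondary point is about the estimate. A half-dosed participant who stays in the AZD7442 analysis contributes roughly half the intended exposure. Treatment A is one injection from one vial, so this cannot happen in A. For A/B and A/C the distortion therefore has one direction: the comparator mean falls and the ratio rises. For B/C it could go either way. No rule in either document names a participant who received only one of the two mAbs.

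**Working it through.** **1. The instructions side by side**

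| Step | Protocol 5.4.5 | Protocol 5.4.6.2 and 5.4.6.3 |
|---|---|---|
| First injection | AZD8895 | AZD8895 |
| Immediate reaction before the second | no further IMP | no exception given |
| Resulting state | AZD8895 without AZD1061 | excluded for every participant |

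The order is fixed, so every use of the 5.4.5 instruction leads to the excluded state.

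**2. Path through the analysis sets**

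The participant is in the safety set. Entry to the PK set turns on whether an important deviation occurred. Against 5.4.5, withholding is compliance; against 5.4.6.2 and 5.4.6.3, it is a dosing deviation. The texts do not settle which reading applies, and even an important deviation leads to exclusion only at discretion. If the participant is kept and AZD1061 is assayed as below the limit, the sum table returns AZD8895 alone.

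**3. The plan's power figure**

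Inputs from Protocol 11.4: 69 per group, true ratio 1, 90% CI within 0.8 to 1.25, and CVs for Cmax of 35.6% (AZD8895) and 38.5% (AZD1061). Stated power: at least 95%.

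- Log-scale SD = sqrt(ln(1 + 0.385²)) = 0.372.
- SE of the log ratio = 0.372 × sqrt(2/69) = 0.0633.
- Normal approximation: 2Φ(0.2231/0.0633 − 1.645) − 1 = 94.0%.
- Exact two one-sided tests, 136 df: 93.8% at CV 38.5%, 96.7% at 35.6%, 96.0% at 36.4%.

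The stated figure is reproduced to within about 1.3 points at the largest CV, without covariate adjustment.

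**4. Effect of retained half-dosed participants**

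Let h be a half-dosed participant's AZD7442 exposure relative to full dose, and k the number of such participants in a comparator arm of 69. The arm's mean log exposure shifts by k × ln(h)/69, so the A/comparator ratio is multiplied by h^(−k/69).

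Take h = 0.5: 150 of 300 mg was given, and Protocol 3.3.2 describes the PK of the two mAbs as similar. For k = 1 the shift is ln(0.5)/69 = −0.0100, a factor of 1.010. For h from 0.4 to 0.6 the factor for one case is 1.013 to 1.007.

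Power at CV 38.5% comes from a simulation of 40,000 unadjusted two-group trials, with the cases in the comparator arm only:

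| k | Ratio factor | Power |
|---|---|---|
| 0 | 1.000 | 93.8% |
| 1 | 1.010 | 93.2% |
| 2 | 1.020 | 91.7% |
| 3 | 1.031 | 89.7% |
| 5 | 1.052 | 83.1% |

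One case also raises the average pooled log SD from 0.371 to 0.376. Excluding one participant instead (69 against 68) leaves power at 93.6%.

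**The case against.** **A general rule and a specific case.** The administration steps can be read as general and the 5.4.5 sentence as an implied exception for one event. Protocol 5.7 also allows IMP to be discontinued for relevant safety changes, so incomplete dosing is contemplated elsewhere. This is a fair reading, but the reader has to supply it. The pairing sentence covers every participant, and no cross-reference limits it. The need to reconcile the texts stands.

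**Exclusion is already possible.** A reader might infer that a stop under 5.4.5 is not a protocol deviation and that the participant would therefore stay in the AZD7442 analysis. The documents do not support either step. Protocol 11.3 defines deviations broadly and includes dosing deviations. Under 5.4.6.2 and 5.4.6.3, giving AZD8895 alone is a departure from the plan. SAP 4.6.2 and 4.5.8 allow participants, or only some of their data, to be left out. Protocol 11.1.3 requires reasons to be documented, and 5.4.5 itself points to possible exclusion under 11.1.3. This objection stands to the extent that the participant could stay, not that the participant would. What remains is that each route is discretionary and none names this case, in an open-label study.

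**Redundancy and size.** No separate rule is needed for the mAb not given: AZD1061 would be expected to be unquantifiable and to yield no usable parameters. AZD8895 results are unaffected. Only the sum is at issue, and one case moves it by about 1% against limits of 0.80 to 1.25. All of this stands.

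**Conclusion.** The contradiction between Protocol 5.4.5 and Sections 5.4.6.2 and 5.4.6.3 is plain from the text and rests on no numerical assumption. It matters because it arises during a possible hypersensitivity reaction. The sections must be reconciled; no view is taken here on which instruction is right.

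The analysis point is real but low in impact. A half-dosed participant may or may not be caught by the PK-set filter. If kept, that participant's AZD7442 exposure would be about half the full-dose value and would raise A/B or A/C by about 1% per case, with about 0.6 points of power lost for the first. Several cases in one arm would be needed for a material effect. The documents give no rate for such reactions, so the expected number is unknown.

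These sizes assume:
- equal contribution of the two mAbs to the sum (h = 0.5, range 0.4 to 0.6 shown);
- AZD1061 below the limit of quantification throughout;
- 69 analysed per group and no covariate adjustment;
- the AZD1061 Cmax CV of 38.5% as a stand-in for the CV of the sum, which the documents do not give.

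**What to change.** 1. **Protocol 5.4.5, 5.4.6.2 and 5.4.6.3:** reconcile the wording so that a single instruction applies when a reaction occurs between the two injections, and add a cross-reference. The choice of instruction belongs to the sponsor's clinical and safety functions.
2. **SAP 4.5.3:** state that a participant who received only one of the two mAbs is excluded from the AZD7442 (sum) analysis, while data for the mAb received are kept. This should apply whether or not the case is classed as a protocol deviation.

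The cost is about one sentence in each affected section. No extra data are needed. By the calculation above, excluding one such participant costs about 0.2 points of power (93.8% to 93.6%), less than keeping the participant would cost.
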